### 6.4 STUDY INTERVENTION COMPLIANCE

A participant will be considered a drop if they miss 4 therapy sessions in a row. Up to two sessions per week can be conducted to make up previously missed weeks. No more than 4 sessions will be completed before week 4, no more than 7 sessions will be complete before week 7, no more than 11 sessions will be complete before week 11. At week 8 onward, clinical response WILL be assessed and discussed with participant to determine if therapy is complete or will continue. No Therapy sessions will be held in wk 16.

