#### **6.1.2 DOSING AND ADMINISTRATION**

##### **MBCT/BATA Therapy Window Visits:**

Therapy sessions will be managed overall by calendar weeks, rather than trying to count days. This study is offering up to 15 weeks (as opposed to sessions) of treatment. Therapists will be instructed that they need to push to schedule at least one appointment per week, even if it's not on the same day of the week each week. The therapy portion of the study will follow this protocol:

Therapy Week	Procedures & Window
Week 0	The week the first MRI scan takes place. This "starts the clock" for both therapy and assessments
Weeks 1-3	Weekly therapy sessions. Sessions can start post-scan in week 0 if preferred; up to two sessions can be scheduled in a calendar week to make up missed sessions, with no more than three sessions completed by the end of week 3. Therapy content will not be skipped: for example, the content designated for Session 1 will be administered at the first therapy session, regardless of the week in which it takes place.
Week 4	Follow-up REDCap Questionnaires, computer tasks, and therapy. REDCap questionnaires and computer tasks will take place in this week as long as at least one session was attended in weeks 0-3. If 0 sessions were attended prior to this week, assessment is delayed to Week 5. If a subject has not attended at least one therapy session by the end of Week 4, they are a study drop by the 4-miss rule. This way every subject will have at least one "dose" (=therapy session) prior to the Wk4 visit.
Week 5	Weekly therapy session. If necessary, this can be a make-up for the Week 4 assessment if they did not attend or if Week 4 was first therapy session. If the participant does not attend therapy in Weeks 4 or 5, the "Wk4 Assessments" will not be collected and will be considered missing.
Weeks 6-7	Weekly therapy sessions. Up to two sessions per week can be conducted to make up previous missed appointments. No more than 7 Sessions will be delivered by the end of Week 7.
Week 8	Follow-up REDCap questionnaires, computer tasks, therapy, MRI Scan. If the subject has not attended at least 2 sessions overall, including at least 1 session in weeks 5-7, assessments and MRI scan may be delayed to Week 9. If a subject has not attended at least 1 session between weeks 5-8, they are a study drop by the 4-miss rule. Clinical response will be assessed and discussed with participants at this therapy session to determine if therapy is complete or will continue.

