Week 9	Weekly therapy session. If necessary, this can be a make-up for the Week 8 visit and/or MRI Scan. If the participant does not attend therapy and/or MRI scans in Weeks 8 or 9, the "Wk8" assessments will not be collected and will be considered missing. DECISION POINT: The study team proposes that in terms of their best use of study resources, anyone who misses both the Week 4/5 and Week 8/9 Behavioral assessments, as well as the Week 8/9 MRI scan, should be considered a study drop and will be withdrawn from the study at that time.
Weeks 10-11	Weekly therapy sessions. Up to two sessions per week can be conducted to make up previous missed appointments. No more than 11 sessions will be conducted by the end of Week 11. If treatment is completed during one of these sessions, a final Assessment will be conducted at the final therapy session, and the final MRI scan will be scheduled by the end of the week following the final therapy session.

Week 12	Follow-up REDCap questionnaires, computer tasks, therapy, MRI Scan. If subject has not attended at least 3 sessions overall, including at least 1 session in weeks 9-11, assessments and MRI scan may be delayed to Week 13. If a subject has not attended at least 1 session between weeks 9-12, they are a study drop by the 4-miss rule.
Week 13	Weekly therapy session. If necessary, this can be a make-up for the Week 12 assessments and/or MRI Scan. If the participant does not attend therapy and/or MRI scans in Weeks 12 or 13, the "Wk12" assessments will not be collected and will be considered missing. DECISION POINT: Anyone who misses both the Week 8/9 and Week 12/13 Behavioral assessments, as well as the Week12/13 MRI scan, should be considered a study drop and will be withdrawn from the study at that time.
Week 14	Weekly therapy sessions. Up to two sessions per week can be conducted to make up previous missed appointments.
Week 15	Follow-up REDCap questionnaires, computer tasks, therapy, MRI Scan. If the subject has not attended at least 4 sessions overall, including at least 1 session in weeks 13-15, assessments and MRI scan may be delayed to the following week ("Week 16"). No therapy sessions will be held in Week 16.

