## 7.2 PARTICIPANT DISCONTINUATION/WITHDRAWAL FROM THE STUDY

Subjects will be informed that they have the right to discontinue their participation at any time, and that their right to obtain appropriate treatment through normal referral channels will not be affected by their decision to participate or not participate. Subjects will also be informed that they have the right to demand that their responses not be included in the study, and that any publications resulting from the research will not identify them as individuals. The study doctor may decide to take a subject off this study if their condition gets worse, if they have serious side effects, or if the study team determines that it is no longer in the subject's best interest to continue. Other reasons for the study doctor to withdraw a subject from the study includes: if the subject is female and becomes pregnant, the subject needs treatment not allowed in the study (antidepressant, mood stabilizer and/or antipsychotic), the subject misses 4 talk therapy sessions in a row and has not maintained contact with their study therapist or any member of the study team. Though starting a benzodiazepine, sleep or ADHD medication is not encouraged in the study, if the situation arises during the study where it medically indicated by their own doctor that one of these type medications is needed, they will be allowed to start these medications and asked to notify the study team so it can be documented. The reason for participant discontinuation or withdrawal from the study will be recorded on the UNC REDCap tracking log form.

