## 7.3 LOST TO FOLLOW-UP

A participant is considered lost to follow-up if he or she fails to return for four scheduled therapy visits in a row and is unable to be contacted by the study site staff.

The following actions are taken if a participant fails to return for a required study therapy visit:

- The site will attempt to contact the participant and reschedule the missed visit (must complete at least 1 therapy session before week 4 and at least 1 in weeks 5-8 and again at least 1 in weeks 9-12 and 13-15, if applicable). Study team will counsel the participant on the importance of maintaining the assigned visit schedule and ascertain if the participant wishes to and/or should continue in the study.
- Before a participant is deemed lost to follow-up, the investigator or designee will make every effort to regain contact with the participant (where possible, 3 telephone calls and emails, if necessary, these contact attempts should be documented in the participant's study file in REDCap).
- Should the participant continue to be unreachable, he or she will be considered to have withdrawn from the study with a primary reason of lost to follow-up.
- R33-If a participant is unable to return for the task visit due to sickness, weather, travel, etc but is attending the remote therapy sessions, the scheduled week 4, 8 and/or 12 task visit may be skipped, documented as a deviation but the participant is allowed to continue.

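### The missed-therapy drop rule differs between sections, and participants dropped by the team or from week 8 onward have no clearly written post-treatment SHAPS.

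*Combined protocol and SAP*

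**What the plan says.** **Missed therapy.** Section 6.4, repeated in 7.1, gives the general rule without further condition: "A participant will be considered a drop if they miss 4 therapy sessions in a row". The therapy-window table in 6.1.2 checks three calendar blocks: "If a subject has not attended at least one therapy session by the end of Week 4, they are a study drop by the 4-miss" criterion; "If a subject has not attended at least 1 session between weeks 5-8, they are a study drop by the 4-miss rule"; and "If a subject has not attended at least 1 session between weeks 9-12, they are a study drop by the 4-miss rule". Section 7.2 lists, among reasons for the study doctor to withdraw someone, that "the subject misses 4 talk therapy sessions in a row and has not maintained contact with their study therapist" or the team. Section 7.3, on rescheduling missed visits, says participants "must complete at least 1 therapy session before week 4 and at least 1 in weeks 5-8".

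**Missed assessments.** At Week 9, Section 6.1.2 withdraws from the study "anyone who misses both the Week 4/5 and Week 8/9 Behavioral assessments, as well as the Week 8/9 MRI scan"; Week 13 has a decision point of the same form. For R33 participants attending remote therapy, Section 7.3 says that "the scheduled week 4, 8 and/or 12 task visit may be skipped, documented as a deviation but the participant is allowed to continue". Sections 1.1, 4.1 and 4.2 give R33 participants pre- and post-treatment scans only.

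**Assessment after a drop.** Section 4.2 (neuroimaging session) asks those who leave treatment before 8 weeks to return for tasks, questionnaires and MRI. Section 7.1 limits the request to a participant who decides to drop before 8 weeks after at least one session, and names only the brain scan.

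**Analysis.** Section 9.2 analyzes Aims 3 and 4 by a pre/post repeated-measures ANCOVA described as intent-to-treat. SHAPS change is a primary endpoint in Section 1.1.

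**The concern.** A rule that ends participation also decides who has a post-treatment outcome. If it differs by section, a participant's status depends on which page staff consult, and Section 6.3 says therapists and participants know the assigned arm. If a drop also ends outcome collection, the missing SHAPS values belong to people who attended poorly or were taken out by the team, who are unlikely to be a random subset. An analysis called ITT would then lack outcomes for reasons the protocol itself creates. The main risk is bias and an unclear analysis set rather than loss of power.

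**Working it through.** **1. The plan's own figure.** The documents quantify nothing about the drop rule. The nearest figure is the Section 9.1 power for SHAPS, which depends on complete post-treatment data: 65 per group, correlation 0.35, α = .05. For the within-between interaction, λ = f² × N × 2 / (1 − ρ).

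- f = .2: λ = 0.04 × 130 × 2 / 0.65 = 16.0, power 97.8% (stated 98%).
- f = .14: λ = 0.0196 × 130 × 2 / 0.65 = 7.84, power 79.4% (stated 80%).

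Both reproduce. Section 5.4 expects about 81% retention between scans; 0.81 × 105 ≈ 85 per group, above 65. Power is not the issue.

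**2. The therapy rules side by side.**

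| Attendance | 6.4 and 7.1 | 6.1.2 blocks | Other section |
|---|---|---|---|
| Week 1, misses weeks 2–5, attends from week 6 | Drop (4 in a row) | No block empty | – |
| Weeks 1 and 8, misses weeks 2–7 | Drop (6 in a row) | No empty block to week 8 | – |
| Misses 4 in a row, answers calls | Drop | Depends on the weeks | 7.2 reason not met |
| First session in week 4 | Depends on how misses are counted | Accepted | 7.3 minimum not met |

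**3. How often the consecutive and block readings part.** Assumptions: one session per week over weeks 1–12, independent weekly attendance with probability p, q = 1 − p, no make-up or week-0 sessions, both arms alike.

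- Block reading: P(drop) = 1 − (1 − q⁴)³.
- Consecutive reading: P(drop) = 1 − a₁₂, where a₀ = a₁ = a₂ = a₃ = 1 and aₙ = p(aₙ₋₁ + q·aₙ₋₂ + q²·aₙ₋₃ + q³·aₙ₋₄).

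Listing all 4,096 attendance patterns, the consecutive reading drops 1,224 and the block reading 721. All 721 are among the 1,224, so the readings disagree on 1,224 − 721 = 503 patterns, and the disagreement probability is the difference of the two formulas.

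| Assumed p | Consecutive | Block | Disagree |
|---|---|---|---|
| 50% | 29.88% | 17.60% | 12.3% |
| 60% | 14.55% | 7.49% | 7.1% |
| 70% | 5.31% | 2.41% | 2.9% |
| 80% | 1.18% | 0.48% | 0.7% |
| 90% | 0.08% | 0.03% | 0.05% |

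Therapy may end from week 8. Over weeks 1–8 only, disagreement at 70% is 3.08% − 1.61% ≈ 1.5%.

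**4. Week 9 and Week 13 decision points.** Withdrawal needs two missed behavioral assessments and a missed scan. R33 has no Week 8 or Week 12 scan. Either an unscheduled scan cannot be missed and the rule never operates, or its absence counts and the scan condition is always met. The text does not say which, and the R33 exception in 7.3 does not mention the decision points.

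**5. Who has a written post-treatment assessment.**

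- Decides to leave before 8 weeks, at least one session: yes, but 4.2 lists tasks, questionnaires and MRI while 7.1 lists only the scan.
- Dropped by the team before 8 weeks: arguably covered by 4.2, not by 7.1.
- Dropped from week 8 onward, including at the Week 9 or Week 13 decision point: nothing clearly written.

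**The case against.** The strongest reply is that the blocks are checkpoints within the general rule. Section 6.1.2 refers to the 4-miss rule by name, every block drop is also a consecutive drop, and no section says outright that someone who misses weeks 2–7 is kept. Sections 7.1, 7.2 and 7.3 also have different jobs: stopping the intervention, withdrawal by the study doctor, and loss to follow-up. That reading is possible, but the protocol does not state it. Section 6.1.2 lets the Week 8 assessments move to Week 9 when weeks 5–7 were missed, without excluding someone already four misses down. The lost-contact condition in 7.2 and the first-session deadline in 7.3 remain different from their counterparts.

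Some outcome data would survive. Section 4.2 collects SHAPS at each therapy visit, so a last in-treatment value may exist; it allows the final assessment apart from the last session; and it lets those who stop early by agreement complete the self-report at the scan visit. This narrows the gap, but the Section 9.2 model uses pre- and post-treatment values.

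Three stronger readings are tempting and not supported:

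- *Every R33 participant who skips the task visits is withdrawn at Week 9.* The rule also needs a missed scan, 7.3 gives an explicit R33 exception, and the questionnaires can be done remotely, so skipping a task visit is not necessarily missing the assessment.
- *Section 9.2 promises a post-treatment SHAPS to everyone with one session.* That sentence sits under the fMRI aims and refers to BATA sessions.
- *Retention and dose cannot be interpreted.* MBCT attendance is tracked (6.1.1), therapist session notes go into REDCap (10.1.9.1) and withdrawal reasons are logged (7.2).

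**Conclusion.** The concern holds as a defect of specification. The drop rule is stated inconsistently in Sections 6.1.2, 6.4, 7.1, 7.2 and 7.3. The R33 decision points are inoperative or ambiguous. Participants dropped by the team or from week 8 onward have no clearly written post-treatment SHAPS.

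The size depends on adherence, which the documents do not report. Under the assumed attendance model the two main readings disagree for about one participant in eight at 50% attendance and for well under 1% at 80% or more. Ignoring make-up sessions and running everyone to week 12 are simplifications, and real absences may cluster. A reader might infer that dropping will differ by arm; knowledge of the arm makes that possible, but nothing in the documents shows it. No view is taken on which stopping rule is right.

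**What to change.** 1. Reconcile Sections 6.1.2, 6.4, 7.1, 7.2 and 7.3 into one rule chosen by the clinical team, stated once and cross-referenced.
2. Align the Week 9 and Week 13 decision points with the R33 scan schedule and with the R33 exception in 7.3.
3. For data collection only, record stopping therapy separately from withdrawing from the study. Send the post-treatment self-report to every randomized participant who stops therapy, at any week and whoever made the decision, unless consent is withdrawn. Section 4.2 already allows the final questionnaires by emailed REDCap invitation but lists SHAPS separately, so add SHAPS to that invitation explicitly.
4. Make the early-drop visit in 4.2 and 7.1 agree on who is asked and what is collected.

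The cost is protocol wording, a separate tracking-log entry and survey invitations through a system already in use. No new procedures are needed.

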### 6.5 CONCOMITANT THERAPY

Those who are stable on a sleep, as needed benzodiazepine and/or ADHD medication will be allowed in the study are allowed to be in the study and if they need to start one of these medications per their medical doctor, they will be allowed to continue in the study. Any other psychotropic medication for mood, anxiety, OCD, mood lability, etc are not allowed in the study and if needed during the course of the study, will end in participant withdrawal.

#### 6.5.1 RESCUE MEDICINE

*Not-applicable.*

## 7 STUDY INTERVENTION DISCONTINUATION AND PARTICIPANT DISCONTINUATION/WITHDRAWAL

### 7.1 DISCONTINUATION OF STUDY INTERVENTION

A participant will be considered a drop if they miss 4 therapy sessions in a row. Up to two sessions per week can be conducted to make up previously missed weeks.

If a participant decides to drop the study before they reached 8 weeks of therapy and they have completed at least 1 therapy session at the time they withdraw, they will be asked to return for one final visit to UNC to complete a post treatment brain scan.

If a subject who agreed to the PET sub-study, drops out of the study before week 8 of therapy & they have had at least 2 therapy sessions, they will also be asked to do the post PET scan at the time of the 7TMRI & blood at UNC.

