### **Study Visits:**

Potential participants will complete the following:

- 1) A phone or online screen to determine initial eligibility via UNC's REDCap

- 2) A 1-2 clinical characterization visit(s) to determine eligible, and, if eligible, to characterize participants clinically. During COVID, can be split remote/in-person.
- 3) A pre-treatment 7 Tesla (7T) fMRI scan & if one of the first 60 subjects enrolled, have an initial blood draw of 10ml (2tsp). Update, the NARSAD blood protocol had entered an extension and has additional funds so up to 210 participants, in both phases, will have an initial blood draw of 10ml (2tsp). **As of 6/26/20, the blood protocol will no longer continue for any new participant enrolled in the study. As of the NCE 2022, this current amendment, imaging of new participants will end. Only enrollment into the therapy portion at Duke will continue.**
- 4) Patients will then be assigned randomly to the experimental treatment (BATA) or comparison treatment (Mindfulness Based Cognitive Therapy (MBCT)) for approximately 15 weeks of treatment.
- 5) The first 60 patients enrolled (n=30 who receive BATA and n=30 who receive MBCT) will additionally complete two additional, mid-treatment, fMRI scans as well as an additional blood draw at all other MRI visits. The 1st phase of the study entered the R61 no cost extension at the end of the project period & due to limited funds, participants will no longer be receiving up to 4 scans. Participants who consent at UNC on or after 11/1/18 will receive only pre- and post-treatment scans (2 scans total). **The R61 no cost extension has ended and the study has entered the larger R33 phase of the study and participants will continue to receive only pre and post treatment scans (2 total) and no bloodwork will be collected starting summer 2020 for new participants. \*\*No new enrollment to imaging at UNC will occur with the approval of the June 2022 NCE amendment.**
- 6) A post-treatment clinical characterization visit
- 7) A post-treatment 7T scan

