**Neuroimaging session (at the UNC Biomedical Research Imaging Center (BRIC)):**

All scan sessions will be identical. All patients will receive pre- and post-treatment scans. The first 60 patients enrolled (n=30 who receive BATA and n=30 who receive MBCT) will also receive two mid-treatment 7T fMRI scans approximately 8 and 12 weeks after starting treatment. The 1st phase of the study entered a R61 no cost extension at the end of the project period & due to limited funds, participants will no longer be receiving up to 4 scans. Participants who consent at UNC on or after 11/1/18 will receive only pre- and post-treatment scans (2 scans total). **Update: We are in the R33 phase of the study which only has pre- and post-treatment scans (2 scans total).** Patients who drop out of treatment early before reaching 8 weeks of therapy, will be asked to return for 1 final post-treatment visit to complete the computer tasks, self-report questionnaires, and MRI. They will complete this early termination/post treatment visit all at UNC to reduce the burden on participants to have to return to both Duke and UNC.

Equipment: This study will utilize a research-dedicated Siemens Magnetom 7T whole body MR scanner for MRI data collection.

7T Scan Preparation: After arrival at the BRIC, participants will undergo a final MRI screening prior to the reassessed by the BRIC technologist for any potential contra-indications to the scan. If any concerns are raised, participants will not undergo the scan. If the subject is a female of child bearing potential, she will complete a urine pregnancy test administered by UNC BRIC study personnel. If the test indicates that she is pregnant, the scan will not be done. In either situation (failed checklist or + urine pregnancy screen), subjects will be informed of this decision to cancel the MRI and thanked for their time and will no longer be eligible to continue in the study. Alternatively, if participants are cleared, they will begin out-of-scanner training in preparation for the scan.

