Exploratory Connectivity Analyses: Mesocorticolimbic connectivity in central to anhedonia. We will explore task-dependent correlations between ROIs using a psychophysiological interactions approach as in our prior work. Timeseries will be extracted from ROIs using FSL Featquery for each participant and trial type and correlation values will be transformed using a Fisher r-to z transformation. We also conduct whole-brain connectivity analysis, with a particular emphasis on the salience network (i.e., dorsal anterior cingulate cortex, anterior prefrontal cortex, and anterior insula), by segmenting the brain based on a probabilistic atlas, while correcting for multiple comparisons at the familywise error rate of  $p < .05$ .

**Secondary Analysis:** Secondary data analysis will be conducted examining relationship between psychological symptoms and patterns of brain activation in the functional neuro data. Data will be transferred from UNC to Duke to be analyzed by Duke study team members.

**Aims 1 and 5:** Only patients who complete baseline measures will receive BATA, and those who complete at least one BATA session will participate in post-treatment assessments (ITT, estimating ~90% of sample). We will compare fMRI activation in regions of interest at pre- and post-treatment. Primary analyses will address changes in regional brain activation from baseline to post-treatment.

Models will include motion parameters, gender, and age as covariates. The design is a 2 (BATA vs MBCT) X 3 (CN, rACC, amygdala) X 2 (pretreatment vs post-treatment) ANCOVA testing the change from pre- to post-treatment as moderated by treatment group and brain region in the outcome variables controlling for the covariates. Post-hoc comparisons will compare change across each region. Note that CN and rACC activation values are derived from the MID task whereas amygdala activation values are derived from the threat task.

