**Aim 2:** We will analyze whether dose moderates treatment response via regression models that predict change in neural target (CN and dACC) activation from the number of sessions as an indicator of BATA dose. Hierarchical linear modeling where time-in-weeks is treated as a continuous variable nested within subject will provide parameter estimates of the linear, quadratic, and cubic functions for change over time in neural target engagement over the course of treatment. Standard evaluation (e.g., significant at  $p < .05$ ) will guide our selection of the most appropriate function. From these functions, we can estimate both the point in time where the change in target engagement is greatest and where it approaches 0, meaning minimal further improvement is anticipated. Although mid-treatment scans will occur at weeks 8 and 12, we will estimate change continuously so the optimal dosage is not restricted to one of those timepoints.

**Aims 3 and 4:** To evaluate the efficacy of BATA, relative to MBCT, for treating anhedonia, functional outcomes, and behavioral indices of reward sensitivity, we will test for differential change over time between those who receive BATA and those who receive MBCT post-treatment. We will use an intent-to-treat (ITT) analysis for patients who receive BATA relative to those who don't. The ITT model will be a repeated-measures ANCOVA with effects for treatment condition (BATA, MBCT), outcome measure (SHAPS, PRT, etc), time (pre-treatment, post- treatment) and their interactions. The interaction tests will assess mean differences at each time point as well as differences in the degree of change between the groups. This also provides tests of each group relative to their baseline scores. We will include gender and age as covariates in these models. \*\*We will also note any participants who were enrolled in the study and had PRT & EffRT reward tasks data omitted during COVID-19 times.

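### Sections 4.2, 7.1 and 9.2 disagree on who is assessed after stopping therapy, and no procedure collects outcomes after unplanned drops or withdrawals from week 8 on, although the analysis is called ITT

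*Combined protocol and SAP*

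**What the plan says.** Three sections describe assessment after a participant stops.

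- Section 7.1 covers one case: "If a participant decides to drop the study before they reached 8 weeks of therapy and they have completed at least 1 therapy session". For that case the plan is that "they will be asked to return for one final visit to UNC to complete a post treatment brain scan". Nothing else is named for the main study.
- Section 4.2, Neuroimaging session: "Patients who drop out of treatment early before reaching 8 weeks of therapy" are asked back once for the computer tasks, the questionnaires and the MRI. "They will complete this early termination/post treatment visit all at UNC to reduce the burden on participants".
- Section 9.2, Aims 1 and 5: "those who complete at least one BATA session will participate in post-treatment assessments (ITT, estimating ~90% of sample".

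For Aims 3 and 4, section 9.2 says: "We will use an intent-to-treat (ITT) analysis for patients who receive BATA relative to those who don't". The model is a repeated-measures ANCOVA with two time points, pre- and post-treatment. Pre/post change in SHAPS is among the primary endpoints in the synopsis. No method for missing post-treatment values is stated.

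The section 6.1.2 table drops anyone with no session in weeks 9-12. At the Week 9 and Week 13 decision points, a participant who has missed the listed assessments "should be considered a study drop and will be withdrawn from the study at that time". Section 2.3.3 removes participants for symptom worsening, sections 6.5 and 7.2 for medication that is not allowed, and sections 7.2 and 8.1.7 for pregnancy.

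Section 4.1 adds: "No new enrollment to imaging at UNC will occur with the approval of the June 2022 NCE amendment". Enrolment into therapy at Duke continues after that.

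**The concern.** An ITT comparison needs outcomes from the people randomized, including those who stop. Here outcome collection after stopping depends on when the person stopped and on which section staff follow. Therapists and participants know the allocation (section 6.3). The reasons for leaving are attendance, worsening and need for medication, all of which may relate to outcome and may differ by arm. If their post-treatment SHAPS is not sought, the pre/post contrast describes people who kept attending. What is at stake is bias in a primary endpoint rather than power.

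**Working it through.** **1. The plan's own power figure.** Inputs from section 9.1: 65 per group with complete post-treatment data (N = 130), alpha .05, correlation 0.35, two time points. For the group-by-time interaction, lambda = N × f² × m / (1 − rho).

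- f = .2: 130 × 0.04 × 2 / 0.65 = 16.0; power 0.978 (stated 98%).
- f = .14: 130 × 0.0196 × 2 / 0.65 = 7.84; power 0.794 (stated 80%).

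Both reproduce. The power statement is not in error.

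**2. The three rules side by side.**

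| | 7.1 | 4.2 | 9.2, Aims 1 and 5 |
|---|---|---|---|
| Who | decides to leave, at least 1 session | any treatment dropout, no session minimum | at least one BATA session; MBCT not mentioned |
| When | before 8 weeks | before 8 weeks | no limit |
| What | brain scan | tasks, self-report, MRI | post-treatment assessments |
| Where | UNC | UNC | not stated |

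**3. Exit routes checked against these rules.**

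- No session by the end of Week 4 (6.1.2): within 4.2, outside 7.1 and 9.2.
- No session in weeks 9-12: a study drop, with no outcome collection stated.
- Week 9 and Week 13 decision points: withdrawn, with none stated.
- Removal from week 8 on for worsening, medication or pregnancy: none stated.
- Too few sessions by Week 15, or none in weeks 13-15: the Week 15 row lets the assessment move to Week 16, so this group is covered.
- Therapy-only participant leaving before week 8: the visit is placed at a site where that person has no procedures.

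Section 9.2 nominally covers the later exits in the BATA arm, but no visit in the schedule carries it out. The contact attempts in section 7.3 are for rescheduling missed therapy visits and do not ask for outcomes.

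**4. Completeness figures in the plan.**

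- 9.2: about 90%, so 0.10 × 210 = 21 without a post-treatment value.
- 5.4: about 81% from pre- to post-neuroimaging, so 0.19 × 210 = 39.9, about 40.
- 9.1, Aim 1: 25 of 30 = 83.3%.
- 9.1, Aims 3 and 4: 65 of 105 = 61.9%, leaving 40 per arm, or 80.

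These are, in order, an expected assessment rate, past experience with scan sessions, an fMRI attrition allowance and a power input. None counts the exits in step 3.

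**5. What the bias would depend on.** Suppose a fraction p is lost in each arm, and the between-arm effect is Dc in those observed and Dl in those lost. The completer contrast then differs from the all-randomized one by p × (Dc − Dl). Assuming Dc − Dl = 0.5 SD for illustration, p = 0.10 gives 0.05 SD and p = 0.19 gives 0.095 SD. These values use total loss, which also includes refusals, unreachable people and early dropouts who are offered a visit. They show how the bias scales and do not estimate the effect of this gap.

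**The case against.** The case against is substantial, and much of it stands.

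- A reader might infer that nobody who stops from week 8 on can have a post-treatment assessment. The documents do not support that. Section 4.2 (final therapy visit) and the schedule of activities allow the final assessment separately from the last session. The schedule has its own study completion visit with SHAPS. Section 4.2 lets a person who finishes early with the team's agreement do the self-report at the MRI visit. These provisions serve planned or agreed endings. A person who stops attending or is removed is not clearly within them.
- A reader might infer that therapy-only dropouts are barred from follow-up. They are not. Section 4.2 moves the computer tasks to Duke after June 2022, and self-report does not need UNC. The text was simply not updated.
- A reader might infer that the lost information cannot be recovered. SHAPS is taken at every therapy session and the full battery at weeks 4, 8 and 12, so most people who leave late have several post-baseline values. The two-time-point ANCOVA does not use them, and they end at the last attended session.
- A reader might divide 65 by 105, read 38% as expected loss, and derive a bias of 0.38 × 0.5 = 0.19 SD. But 65 is a power input, 0.5 SD is arbitrary, and neither describes the affected groups.
- Timing matters. The synopsis gives 72 months and the first DSMB meeting was on 11/8/17, so by this version (October 2023) few participants may remain for a changed procedure.

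**Conclusion.** The point holds in a limited form. Sections 4.2, 7.1 and 9.2 contradict one another on who is assessed after stopping, and no procedure covers unplanned drops or withdrawals from week 8 on. The UNC-only visit was left unrevised for therapy-only participants. The pre/post SHAPS analysis called ITT therefore risks being a comparison of attenders.

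The size of the bias cannot be derived, because the documents give neither the number of people in these groups nor how their outcomes differ. That missingness is related to outcome is an inference from open allocation and the stated removal reasons. This should be fixed: it touches a primary endpoint and the means of remote collection already exist. It does not by itself invalidate the trial.

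**What to change.** 1. Reconcile sections 4.2, 6.1.2, 7.1 and 9.2 so that one rule says who is assessed after stopping, when, with what and where.
2. State that every randomized participant who stops study therapy, for any reason and at any week, is sent the SHAPS and REDCap self-report by survey invitation on stopping and at the planned Week 15/16 time point, unless consent is withdrawn. Apply the existing suicide-risk procedure in section 2.3.3 to the responses.
3. Distinguish having stopped study therapy from having withdrawn from the study, so that the first does not end outcome collection. No clinical removal rule needs to change.
4. In section 9.2, define the ITT set as all randomized, in both arms.
5. Analyse the weekly SHAPS in a longitudinal model so that people without a post-treatment value still contribute, and state its missing-data assumption.

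The cost is a protocol amendment, some coordinator time and safety cover for remote responses. No new instrument or in-person visit is needed. If follow-up has already ended, items 4 and 5 can still be adopted, with a count by arm of who lacks a post-treatment value and why.
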